#### 1. PROTOCOL SYNOPSIS

The present prospective, single-center trial is designed to evaluate the efficacy of CyMedica Orthopedics e-viveTM system, a multifunctional electrotherapy device providing neuromuscular electrical stimulation (NMES), for improving quadriceps strength and accelerating functional recovery in patients managed with total knee arthroplasty (TKA). This post-market clinical trial will involve fellowship-trained Adult Reconstructive orthopaedic surgeons, and include patients who are receiving a unilateral primary TKA. It is hypothesized that the combined preoperative and postoperative use of the CyMedica e-vive NMES can allow for better knee function and allow for a quicker return to function following TKA.

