#### 1.3 Outcome Assessments

These three groups will be analyzed using several outcome measures including validated patient-reported outcome measures the Knee Injury and Osteoarthritis Outcome Score(KOOS) [1], and Veterans RAND 12 item health survey (VR-12))[2], knee active range of motion (extension, flexion), quadriceps femoris muscle (QFM) strength, the Timed Up and Go Test [3] and the Stair Climb Test. The primary endpoint for the study is QFM strength. However, of secondary interest will be: 1) other physical performance measures (i.e. limb symmetry index and gait speed, activity levels), 2) Visual Analogue Scale (VAS) pain levels [4], on outpatient follow-up and immediately before & after NMES therapy, 3) length of stay, 4) Patient dependence on assistive device, 5) Patient satisfaction measures, 6) Patient discharge disposition, 7) Patient readmission rate. The proprietary app for this product will be used to track device usage (intensity, duration of session, frequency of use), knee range of motion and gait speed.

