### 3. HYPOTHESIS AND SPECIFIC AIMS

**Study Hypothesis:** Our hypothesis is that use of the CyMedica e-viveTM NMES both preop and postop can improve functional outcomes following TKA.

**Specific Aim 1.** Test whether patients treated with preop and postop NMES show improved physical performance measures when compared to postop only NMES group and standard of care group.

**Specific Aim 2.** Test whether patients treated with preop and postop NMES show improved patient-reported outcomes when compared to postop only NMES group and standard of care group.

**Specific Aim 3.** Test whether patients treated with NMES require fewer outpatient physical therapy visits when compared to the standard of care group.

**Specific Aim 4.** Test whether patients treated with NMES have a decreased discharge disposition to extended care facilities as well as shorter length of stay in extended care facilities compared to standard of care group.

**Specific Aim 5**. Test whether patients treated with NMES have decreased 90 day postoperative readmission rates compared to the standard of care group.

**Specific Aim 6.** Test whether patients treated with NMES have decreased dependence of the use of ambulatory assist devices.

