#### 6.3 Assessments

#### **Data collection**

The study duration will be until 12 weeks  $\pm$  1 week postoperatively. Data will be collected (1) 4 weeks preoperatively, (2) prior to hospital admission for TKA, and (3) at 3, 6, and 12 weeks postoperatively (see table in 1.4). All data will be entered and maintained in REDCap, an electronic data capture tools hosted at Cleveland Clinic [20].REDCap (Research Electronic Data Capture) is a secure, web-based application designed to support data capture for research studies, providing 1) an intuitive interface for validated data entry; 2) audit trails for tracking data manipulation and export procedures; 3) automated export procedures for seamless data downloads to common statistical packages; and 4) procedures for importing data from external sources. Only members of the study team (i.e. the personnel listed on the IRB application) will have access to protected health information of patients included in this study.

The following will be collected on all patients in the study and managed using REDCap:

- 1 MRN
- 2. Name
- 3. Date of birth
- 4. Address
- 5. Phone number
- 6. Email address
- 7. Date of surgery
- 8. Visit dates
- 9. Age at the time of surgery
- 10. Gender: male or female
- 11 BMI
- 12. Comorbidities
- 13. Date of surgery: (month/day/year)
- 14. Any complications (e.g., emergency department visits, infection, reoperation, etc.)
- 15. KOOS, VR-12, and VAS pain questionnaire forms

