### 7. CLINICAL OUTCOMES

# 7.1. Sample Size Justification

A recent review paper written by Maddocks et al looked at eight different studies that used quadriceps muscle strength as an outcome and created a pooled analysis. They found a standardized mean difference of 0.90 for quadriceps muscle strength between control and NMES intervention groups. Sample size was calculated using this standardized mean difference, along with 80% power and the level of significance (p-value) set to 0.05. This study will require 20 patients per group. However, adding in a 10% expected dropout rate, planned enrollment will be 22 patients per group for a total enrollment of 66 patients.

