# 7.2. Statistical Analysis

Data will be analyzed using intent-to-treat methodology (Herman et al JBJS 2009), utilizing the original treatment group to which a patient was assigned. Differences between means will be analyzed using Student's t-test, while categorical variables will be tested using frequency tabulations comparing outcomes between treatments with the Pearson chi-square test. Differences will be considered significant at the level of  $p \le 0.05$ .

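### The primary endpoint, QFM strength, has no primary visit, contrast order or success criterion, so its false-positive rate is not fixed at 5%

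*Combined protocol and SAP*

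**What the plan says.** Section 1.3 states "The primary endpoint for the study is QFM strength". It attaches no visit, change score or summary measure. Section 6.3 schedules postoperative data collection "at 3, 6, and 12 weeks postoperatively", and the table in section 1.4 lists QFM strength at each of those visits as well as at the two preoperative time points. Section 1.1 sets up three arms: combined, postoperative-only and standard of care.

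Aim 1 in section 3 asks whether the combined arm shows "improved physical performance measures when compared to postop only NMES group and standard of care group". That names two contrasts and ranks neither. The study hypothesis in the same section is that NMES used "both preop and postop can improve functional outcomes following TKA", and the synopsis expects it to "allow for a quicker return to function following TKA".

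Section 7.1 takes a standardized mean difference (SMD) of 0.90 "for quadriceps muscle strength between control and NMES intervention groups", "along with 80% power and the level of significance (p-value) set to 0.05". This gives 20 patients per group, or 22 after allowing for 10% dropout.

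The analysis plan in section 7.2 consists of intention-to-treat, a t-test for means, a chi-square test for categories, and the sentence "Differences will be considered significant at the level of" p ≤ 0.05. No section gives a primary visit, an order of contrasts, a rule for declaring success or any multiplicity control.

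**The concern.** A two-sample t-test needs a pair of arms and a visit, and the plan supplies neither for its primary endpoint. The two Aim 1 contrasts at three postoperative visits make six tests of QFM strength, each at 0.05, with no rule for combining them.

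The error rate of the trial then depends on a rule that nobody has written. If a win at any visit is enough, the 5% level does not hold even for a single contrast. If both contrasts must succeed, the error is low when no arm has an effect, but the chance of success is well below the power of one comparison. Because the choice is open, it could be made after the results are seen, and a reader could not tell what a positive trial means.

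**Working it through.** **Inputs from the documents.** SMD 0.90, 80% power, level 0.05 and 20 evaluable per arm (section 7.1); 1:1:1 allocation (section 5.4); visits at 3, 6 and 12 weeks (sections 1.4 and 6.3); two contrasts (Aim 1, section 3); t-test at p ≤ 0.05 (section 7.2).

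**Assumption.** The documents give no between-visit correlation for QFM strength. It is taken as 0.5 to 0.8, with 0.3 and 0.9 as wider limits.

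**The plan's own figure.** n per arm = 2(z₀.₉₇₅ + z₀.₈₀)²/SMD² = 2(1.960 + 0.842)²/0.81 = 19.4, rounded up to 20. This reproduces section 7.1. A one-sided level would give 2(1.645 + 0.842)²/0.81 = 15.3, that is 16, so the stated 0.05 is two-sided and the nominal rate in the favourable direction is 2.5%. With the exact t-distribution, power at 20 per arm is 79.2%. Enrolment: 20 × 1.1 = 22.

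**Ceiling by hand.** If the tests were independent, the chance of at least one p ≤ 0.05 would be 1 − 0.95³ = 14.3% for one contrast at three visits, 1 − 0.95² = 9.75% for two contrasts at one visit, and 1 − 0.95⁶ = 26.5% for all six. The tests are positively correlated, through repeated visits and the shared combined arm, so the true rates are lower.

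**Simulation.** Three normal arms of 20, three equally correlated visits, pooled two-sample t-tests at two-sided 0.05, 100,000 to 200,000 trials per setting. The first table assumes no effect in any arm. Pairs of figures are for correlation 0.5 / 0.8.

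| Rule for success | Favouring combined | Either direction |
|---|---|---|
| One contrast, one visit (nominal) | 2.5% | 5% |
| One contrast, any of three visits | 6.3% / 5.0% | 12.6% / 10.0% |
| Either Aim 1 contrast, one visit | 4.5% | 9.1% |
| Either Aim 1 contrast, any visit | 11.1% / 8.8% | 22.1% / 17.6% |
| Both contrasts, one visit | 0.45% | 0.9% |
| Both contrasts, any visits | 1.5% / 1.2% | 3.2% / 2.3% |

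At correlation 0.3 and 0.9, the either-direction rate in the fourth row is 23.7% and 15.1%.

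**When the postoperative-only arm works as well as combined** (both SMD 0.90 over standard of care), the chance of wrongly claiming both contrasts is 6.3% / 5.0% with the visit open, against 2.5% at one fixed visit.

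**Power at one fixed visit, SMD 0.90 for combined over standard of care.**

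| True postoperative-only effect | Win the first contrast | Win both |
|---|---|---|
| None | 79.2% | 67.7% |
| Half (SMD 0.45) | 79.2% | 26.7% |

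**Fixed-order testing at one visit.** The family-wise error is 5.0% with no effect in any arm, and 3.5% when postoperative-only equals combined at SMD 0.90.

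**The case against.** The strongest reply is that the contrast is less open than it looks. Section 7.1 powers a control-versus-NMES difference, and section 4.1 makes the control group standard of care, so combined versus postoperative-only cannot be the powered pair. Aim 1 and the study hypothesis centre on the combined arm. The one pair that fits both is combined versus standard of care. This stands as an inference, though the plan never states it. It does not settle the visit: 12 weeks is the last one, but a claim of quicker recovery could equally point to 3 or 6 weeks.

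A reader might infer that the trial has a 17–22% false-positive rate. The documents do not support that. It is an either-direction figure for the most permissive reading of Aim 1, in which any one win counts, and no such rule is written. Aim 1 joins its comparators with 'and', which suggests that both are needed. Counting the third pair as well would give about 23–29%, but section 7.2 lists no comparisons and Aim 1 does not name that pair.

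A reader might also infer that the 68% and 27% contradict the stated 80% power. They do not. Section 7.1 gives 80% for one control-versus-NMES difference and never claims it for winning both contrasts.

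The multi-visit rates do rest on an assumed correlation, and the plan does not say whether raw values or changes from baseline are compared. If baseline is correlated with each visit as strongly as the visits are with each other (r), changes from baseline correlate at (1 − r)/(2 − 2r) = 0.5, which is inside the range used.

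Finally, this is a 66-patient, post-market, investigator-initiated trial. That bears on how elaborate the remedy should be, but a primary endpoint still needs a decision rule, and the remedy here is short.

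**Conclusion.** The point holds. The plan has one primary endpoint, three arms and three postoperative visits, and its only decision rule is p ≤ 0.05 per test. Combined versus standard of care is the most natural main contrast by inference; the visit is open on any reading.

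On that inferred contrast alone, the open visit doubles the nominal 2.5% favourable error or slightly more, to about 5–6%. Letting either Aim 1 contrast count takes it to about 9–11%. Requiring both brings it down to 1–2% if no arm has an effect, but that is not the worst case for this rule: it is 5–6% if postoperative-only truly matches combined. The spread between these rules is the problem, because the plan does not choose one.

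The multi-visit figures assume 20 per arm, normal outcomes and a between-visit correlation of 0.5–0.8. Within the wider limits run (0.3 to 0.9) the conclusion does not change.

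**What to change.** Amend sections 7.2, 1.3 and 7.1 together, before any outcome comparison:

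1. Name one primary visit for QFM strength, for example 12 weeks, or an earlier one if faster recovery is the main claim. Make the other visits secondary.
2. At that visit, test combined versus standard of care at two-sided 0.05. Only if it is significant, test combined versus postoperative-only at two-sided 0.05.
3. State the success criterion. The trial is positive for combined NMES over standard of care if the first test succeeds in its favour. A benefit of adding preoperative NMES is claimed only if the second test also succeeds.
4. State in section 7.1 that the sample size and its 80% power refer to combined versus standard of care only.

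The cost is a short amendment, with no extra patients or measurements. At SMD 0.90, power is about 79% for the first contrast. The chance of claiming both is about 68% if postoperative-only has no effect and about 27% if it has half the effect. Nothing can be claimed on the second contrast if the first fails, which is a real price given the trial's interest in preoperative use. Results at the other visits cannot carry the main claim.

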### 8. PATIENT INCENTIVE PLAN

In an effort to help bring patients back for all visits and increase device use compliance, patients will be offered \$25 for the 3, 6, and 12 week postoperative visits. In addition, those patients who maintained 80% compliance will be offered a \$200 gift card at the end of the study. The maximum amount a patient may receive is \$275. In addition, parking will be provided for each postoperative visit (\$10/per visit). All patients will be given an activity monitoring device made by Misfit Wearables® at the beginning of the study.

# 9. ADVERSE EVENTS

# **Adverse Events and Data Monitoring Committee (DMC)**

The Institutional Review Board requires Investigators to monitor and report Adverse Events. The Institutional Review Board is responsible to assess changes in risk to ensure safety protections of human subjects.

#### **DEFINITIONS**

An Unanticipated Problem Involving Risks to Participants or Others is any event that (1) is unforeseen, (2) caused harm or placed a person at increased risk of harm, and (3) is related to the research procedures.

An Adverse Event (AE) is any untoward or unfavorable medical occurrence, including any abnormal sign (for example, abnormal physical exam or laboratory finding), symptoms, or disease. Adverse events can encompass both physical and psychological harms.

An Internal Adverse Event (AE) is an untoward medical occurrence, which occurs to participants in research conducted by Cleveland Clinic and/or Cleveland Clinic is the IRB of record.

**External Adverse Event (AE)** is an untoward medical occurrence experienced by subjects enrolled at other institutions for the same study approved at Cleveland Clinic or a different study using the same study drug/device.

A Serious Adverse Event (SAE) is any adverse experience that results in any of the following outcomes:

- death
- a life-threatening experience
- inpatient hospitalization or prolongation of existing hospitalization
- a persistent or significant disability/incapacity a congenital anomaly/birth defect
- Important medical events that may not result in death, be life-threatening, or require hospitalization may be considered a serious adverse drug experience when, based upon appropriate medical judgment, they may jeopardize the patient or subject and may require medical or surgical intervention to prevent one of the outcomes listed in this definition.

An Unexpected Adverse Event means any AE not previously known or included in the current Investigator's Brochure, consent form or other risk information.

Related/Possibly Related means there must be reasonable evidence to suggest the event was

caused by the drug, device or investigational intervention.

- 1. Internal Serious Adverse Events (events that occur to participants enrolled in research being conducted by Cleveland Clinic or when Cleveland Clinic is the IRB of record) must be promptly reported to the IRB using the IRB AE Report Form within 10 working days from discovery/awareness which meet any of the following criteria as assessed by the PI/Co-I: a) Serious, Unexpected and Related/Possibly Related.
- b) AE's determined to be occurring at a significantly higher frequency or severity than expected.
- c) Other Unexpected AE's, regardless of severity, that changes the risk benefit ratio of the study and results in changes to the Research Protocol or Informed

### Consent process/document.

All Internal SAEs are also reported at continuing review using the AE Summary Log.

- 2. **External Serious Adverse Events** (events experienced by subjects enrolled at other institutions for the same study approved at Cleveland Clinic or a different study using the same study device/drug) are reportable to the IRB using the IRB AE Report Form within 10 working days from discovery/awareness when:
- a. The External SAE report includes reasonable evidence as assessed by a central monitoring entity [Coordinating or Statistical Center, or a Data Safety Monitoring Board (DSMB) or Data Monitoring

Committee (DMC)] that the event is Serious, Unexpected, and Related/Possibly Related AND places the subjects or others at a greater risk of physical or psychological harm than was previously known or recognized. This will require a change in the protocol and/or consent document.

b. External SAE reports provided by the Sponsor to the investigator indicating the event is Serious, Unexpected and Related/Possibly related but without reasonable evidence or DSMB/DMC determination of greater risk are not reportable to the IRB within the 10 day window. Without Sponsor evidence or assessment the implications of the event cannot be determined by the research team and therefore need not be reviewed. These SAE' shall be placed on

the AE Summary log to be submitted at the annual continuing renewal.

- 3. **DEATHS** are to be reported to the IRB using the IRB AE Report Form according to the following guidelines:
- a) Internal Death
  - Related/possibly related whether expected or unexpected—within 5 working days from discovery/awareness
  - not related and expected at time of continuing review
  - Not related and unexpected at time of continuing review except cancer studies Cancer: Not related and unexpected within 10 working days from discovery/awareness
- b) External Death

Related/possibly related and unexpected – within 5 working days from discovery/awareness not related whether expected or unexpected – at time of continuing review related/possibly related and expected – at time of continuing review

- c) ALL Deaths are also reported at time of continuing review using the AE summary log.
- 4. **Non-serious Adverse events** (Internal and External) that are both Related/Possibly related and unexpected are reported on the AE Summary Log at time of continuing review to assess trends.
- 5. An IRB staff (a qualified, licensed practitioner assigned to this function by the IRB chair and IRB Executive Director) reviews Adverse Event Reports to determine whether they represent Unanticipated Problem Involving Risks to Participants or Others. Events that are assessed, by either the IRB Staff or Investigator, to place subjects or others at a greater risk of harm than was previously known or recognized, or changes the risk/benefit ratio of the study, or requires a change in the protocol and/or consent document are referred to Full Board for review under Policy #70.

Events that do not involve risk to Participants or Others or changes to the informed consent or protocol do not require further review. Investigators are informed of the determination and the IRB file is updated.

6. The AE Summary Log is reviewed by the IRB at the time of continuing review to identify trends in frequency and severity which may impact subject safety.

This study is an Investigator Initiated research trial. Each study site will be considered its own regulatory sponsor and is responsible for internal data monitoring and any study reporting required by ClinicalTrials.gov.

# Appendix A

Timed up and go test (TUG test)

# Set up

- 1. Wrist watch with second hand or stop watch to time performance
- 2. Standard arm chair (approximate seat height of 46 cm, straight back)
- 3. Line on floor 3 meters from chair

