### 1.1 Number Of Sites And Number Of Patients

The study will be conducted at two sites within the Cleveland Clinic Health System (Main Campus, Lutheran Hospital, and Avon Hospital), and involve a total of 66 patients. All study patients will be divided into three groups: (a) NMES therapy both before and after surgery in addition to standard of care physical therapy (PT); (b) NMES therapy only after surgery in addition to standard of care PT; (c) only standard of care PT.

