# **Pretreatment Assessments**

Before treatment, the following assessments/tests will be performed and the results will be recorded on the appropriate pages of the CRF, and or Microsoft excel, Microsoft Word, and REDCap:

- Eligibility criteria, including written informed consent
- Age, gender, height/weight/BMI
- Concomitant diseases
- Physical examination
- Baseline range of motion of affected knee
- Baseline timed up and go test (TUG test, detailed in Appendix A and as described by Podsiadlo et al.)

- Baseline Stair Climb test
- Baseline QFM strength
- Baseline Modified KOOS and VR-12 assessments
- Baseline VAS pain score
- Current medications
- Any use of ambulation assist device

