### Procedure

- 1. Subject wears his regular footwear and uses his customary walking aid.
- 2. No physical assistance is provided.
- 3. Subject starts with his back against the chair, his arms resting on the chair's arms, and his walking aid at hand.
- 4. Instruct subject that, on the word 'go', to get up and walk at a comfortable and safe pace to the line on the floor, turn, return to the chair, and sit down again.
- 5. Allow subject to practice the test once before being timed to become familiar with the test.

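### Appendix A lets the TUG be timed by a wrist watch's second hand and sets no recording precision: a small loss of precision in a non-primary outcome that a wording change would avoid

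*Combined protocol and SAP*

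**What the plan says.** Appendix A (Set up) gives the timing equipment for the TUG as "Wrist watch with second hand or stop watch to time performance". The two instruments are equal alternatives. Neither Set up nor Procedure states a recording precision or asks for the same instrument throughout.

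On repetitions, the Procedure says only: "Allow subject to practice the test once before being timed to become familiar with the test". The number of timed runs and the scoring rule are not stated.

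TUG is a named outcome in section 1.3 and is scheduled at all five time points in section 1.4. It is not primary: "The primary endpoint for the study is QFM strength". Section 1.1 names three hospitals ("Main Campus, Lutheran Hospital, and Avon Hospital"), although it counts two sites. No section says at which of them testing takes place.

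Appendix A is the only written procedure for an outcome test. Section 6.3 (Pretreatment Assessments) points to it for TUG ("TUG test, detailed in Appendix A"). The same list has "Baseline QFM strength" and "Baseline Stair Climb test" with no such pointer.

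**The concern.** A sweep second hand is normally read to the whole second, at the start, at the stop, or at both. A stop watch shows elapsed time in fractions of a second. Allowing either one admits rounding error that the trial need not have, and lets its size vary by patient, visit and tester. Rounding error of this kind is random and cannot be recovered at analysis. At stake is some precision in the comparison of TUG between arms, which is one of the physical performance measures behind Specific Aim 1.

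**Working it through.** **The plan's own figure.** Section 7.1 uses a standardized mean difference (SMD) of 0.90, 80% power and a significance level of 0.05. Two-sided, by the normal approximation:

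n = 2 × (1.960 + 0.842)² / 0.90² = 19.4, so 20 per group, as stated. (The t-based solution is 20.4, so 21.)

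Then 20 × 1.10 = 22, and 3 × 22 = 66, also as stated. The only effect-size input is the SMD for quadriceps strength ("They found a standardized mean difference of 0.90 for quadriceps muscle strength between control and NMES intervention groups"). No TUG quantity enters, so TUG timing cannot alter this figure.

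**Rounding error.** Rounding one reading to the nearest second gives an error uniform over 1 s, with variance 1/12.

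- One end rounded (for example, the start signal given on a tick): SD = √(1/12) = 0.29 s.
- Both ends rounded independently: variance 1/12 + 1/12 = 1/6, SD = 0.41 s.
- Stop watch read to 0.1 s: SD = 0.1/√12 = 0.03 s, which is negligible.

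The tester's reaction time adds error with either instrument and is left out.

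**Effect on TUG variance.** Inflation = error variance / SD². The TUG SD is an assumption, because the documents give none. The third results column is 40 / (1 + inflation), for a comparison of two arms of 20. The last column is the power at an SMD of 0.90 with 20 per group, Φ(0.90 × √10 / √(1 + inflation) − 1.96). That SMD is borrowed purely for illustration, since the plan states no TUG effect. Without rounding error the power is 81.2%.

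| Assumed TUG SD | Inflation, one end | Inflation, both ends | 40 patients are worth (both ends) | Illustrative power (both ends) |
|---|---|---|---|---|
| 1 s | 8.3% | 16.7% | 34.3 | 75.0% |
| 1.5 s | 3.7% | 7.4% | 37.2 | 78.4% |
| 2 s | 2.1% | 4.2% | 38.4 | 79.6% |
| 3 s | 0.9% | 1.9% | 39.3 | 80.5% |
| 5 s | 0.3% | 0.7% | 39.7 | 81.0% |

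The both-ends figures are upper limits at each SD. They assume that every patient is timed by second hand. If only a fraction p of patients are, the average inflation is about p times the figure shown.

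**The case against.** The strongest reply is that this is close to a matter of preference. A stop watch is already allowed and may be what every tester uses. Appendix A follows a published description of the test. At an SD of 2 s or more, the loss is under 2 points of power even in the worst case. All of that stands, and it is why the point is minor. It does not defend keeping the wrist-watch option, which gains the trial nothing.

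Four stronger readings are tempting, and the documents do not support them.

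- **The TUG is timed in a single run.** The Procedure fixes one practice and is silent on the number of timed runs. A single run is possible but not prescribed.
- **Coarse timing could inflate false positives.** A 0.5 s lean in reading would raise the two-sided 5% error rate to about 18%, 12% or 8% at SDs of 1.5, 2 or 3 s, but only if the lean differed consistently between arms. A lean common to all arms cancels. The documents do not say whether testers know the allocation, and nothing in them points to such a difference. A stop watch would not remove a tester's discretion either.
- **The missing strength procedure costs the primary analysis a known amount of power.** If extra test variation added 10%, 25% or 50% to the variance, t-based power would fall from 79% to 75%, 70% or 62%. But 0.90 is a pooled SMD from eight studies, so ordinary measurement error is already in it. Only error in excess of those studies counts, and the documents give no basis for any value.
- **Differences between hospitals or instruments are beyond repair.** Stable differences could be adjusted for by site or by a pre-surgery value, and under 1:1:1 randomization they are noise rather than bias in expectation. Only the random rounding error is irrecoverable.

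**Conclusion.** The point holds as a minor one about TUG. Where the second hand is used, whole-second reading adds an error SD of 0.29 to 0.41 s and raises the TUG variance by at most 7.4%, 4.2% or 1.9% at assumed SDs of 1.5, 2 or 3 s. It would matter more only if the SD were near 1 s. The size rests on the assumed SDs, on independent rounding at the two ends, and on how often a second hand is used in practice, which is unknown. The 20 per group is unaffected.

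The secondary note is true but does not carry the point. Sections 1.3 and 6.3 give QFM strength by name only, with no instrument, test position, number of efforts, scoring rule or unit. The knee-flexion range in section 6.2 is for using the stimulation device, not for testing strength. Trained testers may well fill the gap sensibly, and a manual or case report form outside these documents may already do so. A reader should not infer that the primary result is compromised.

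**What to change.** In Appendix A (Set up), delete the wrist-watch alternative. Require a stop watch read to 0.1 s at every visit and every hospital. The cost is one line of wording, since the stop watch is already on the equipment list, and there is no added burden on patients.

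In the same edit, state how many timed runs are made and which time is recorded. The choice can be left to the investigators, provided that it is fixed in advance.

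Separately, section 6.3 should state or cite a test procedure for QFM strength and require the same method for each patient at all visits. The Stair Climb Test, which also has none, could be covered at the same time. If a manual already exists, a citation is enough. If not, the work is a page per test, and the choice of instrument, efforts and unit is for the investigators.
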